PROTOCOL

Effect of Postoperative Oral Carbohydrate Administration in Total Knee Arthroplasty

Patients

October 16, 2022

Effect of Postoperative Oral Carbohydrate Administration in Total Knee Arthroplasty

1. Research background

In recent years, the concept of accelerated rehabilitation surgery (enhanced recovery after surgery, ERAS) has developed vigorously, using a series of optimized evidence-based medical support with preoperative, intraoperative and postoperative programs to reduce postoperative physiological and psychological stress trauma response, so as to achieve the goal of accelerating patient rehabilitation^[1]. Perioperative fasting water ban management is an important component of ERAS. Studies have found that prolonged preoperative drinking and fasting will increase the postoperative insulin resistance, cause hypertension, and increase the risk of postoperative infection, which is not conducive to the postoperative recovery of^[2]. Oral carbohydrates for at least 2h before anesthesia can reduce the perioperative stress response, improve patient comfort and satisfaction, and promote the postoperative rehabilitation of^[3]. The^[4] of the Chinese Expert Consensus and Path Management Guide for Accelerated Rehabilitation Surgery (2018 edition) advocates the early postoperative recovery of diet. Studies have shown that the early recovery of oral eating, drinking water and early oral assisted nutrition after elective abdominal surgery can promote the recovery of intestinal motor function, help to maintain intestinal mucosa function, prevent microflora imbalance and displacement, and can reduce the incidence of postoperative infection and shorten the postoperative hospitalization time by^[5]. At present, shortening the perioperative water fasting time needs to be concentrated in the preoperative stage. Although the guidelines and a small number of studies recommend the early recovery of diet after surgery, there is no clear stipulation on the recovery time of postoperative diet and drinking water, and most domestic hospitals still perform fasting for at least 6h after surgery.

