1.1 Study Purpose

1.1.1 Main study objective: To evaluate the effect of oral carbohydrates early after TKA on the nutritional status of elderly patients.

1.1.2 Secondary study objectives: To evaluate the effect of early oral carbohydrate administration on the comfort and safety of TKA in elderly patients.

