1.2.2 Secondary study endpoints

1.2.2.1, Effectiveness study endpoint

- 1) The level of retinol-binding protein in venous blood on the day and 1d and 3d after surgery;
- 2) The insulin resistance index in venous blood was checked on the empty stomach on the morning, 1d and 3d after the operation;
- 3) NRS score of thirst and hunger at 2h, 6h and 8h after surgery;
- 4) Abating distension within 24h after surgery;
- 5) The incidence of hypoxemia and reflux aspiration within 24h after surgery;
- 6) Time of anal exhaust for the first time after surgery;
- 7) Time to leave bed for the first time after surgery;
- 8) Length of hospitalization;
- 9) Postoperative subject satisfaction score.

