1.2.2.2. Safety study endpoint

- 1) The incidence and severity of various adverse events (AE) from the start of oral carbohydrates to the end of the trial;
- 2) The incidence and severity of adverse events such as nausea, vomiting and hypoxemia from the first start of drug administration to the end of the trial;
- 3) Number of antiemetic drugs used within 24h after the first start to the first start of drug administration;

2. Expected results

Oral carbohydrates in the early postoperative period can improve patient nutritional

status, improve comfort and satisfaction without increasing the incidence of adverse events.

3. Design and method of the study

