the PACU into two study groups: early carbohydrate feeding group (EOF group) and conventional feeding group (control group). Routine feeding group (Group C): Patients in group C were observed with 60min of abnormal vital signs after extubation, and returned to the ward for fasting and fasting for at least 6 h, and began to eat gradually through the mouth after anal exhaust. Early carbohydrate feeding group (EOF group): The EOF group drank 10.5% of 5 ml/kg body weight (100ml containing 12.5g maltodextrin, fructose and glucose) after extubation in the resuscitation room. PACU management: Patients will randomly enter the PACU into two study groups: early carbohydrate feeding group (EOF group) and conventional feeding group (control group). Routine feeding group (Group C): Patients in group C were observed with 60min of abnormal vital signs after extubation, and returned to the ward for fasting and fasting for at least 6 h, and began to eat gradually through the mouth after anal exhaust. Early carbohydrate feeding group (EOF group): The EOF group drank 10.5% of 5 ml/kg body weight (100ml containing 12.5g maltodextrin, fructose and glucose) after extubation in the resuscitation room.

To evaluate the drinking criteria for patients in the EOF group: Steward wake score of 6 and wake level level 3, take 5 ml/kg body weight of 12.5% carbohydrate (100ml containing 12.5g maltodextrin, fructose, and glucose) according to the patient's consent. The process of drinking carbohydrates was to take 30ml orally first. After observing the swallowing without abnormality, the patient was ordered to drink the remaining drinks within 2h. After the patient returned to the ward, the liquid diet began to gradually overenter the normal diet. When the patient was able to tolerate the normal diet, v.

Evaluation process of the drinking index:

1. Steward score: Akefulness: 0-no response to stimulus; 1-some response to stimulus; 2-full awake.(2) Respiratory tract patency degree: 0 points-the patient's respiratory tract needs support; 1 points-the patient's respiratory tract can maintain patency without support; 2 points-the patient can cough according to the doctor's guidance.(3) Body activity degree: 1 points-the patient's limb has no activity; 2 points-the patient's limb has an unconscious activity; 3 points-the patient's limb can carry out conscious activities

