2. Wakefulness classification according to the patient's consciousness performance: Level 0: the patient is completely asleep, Call without any response; Level 1: The patient is falling asleep, However, head and neck movement, eye opening or limb movement when breathing; level 2: the patient is awake, Have the same performance as level 1, At the same time can also open the mouth, stretch the tongue; Level 3: The patient is awake, Have the same performance as level 2, At the same time can also clearly say their own name, age and other information; Level 4: The patient is awake, Have the same performance as level 3, It can also accurately identify the surrounding environment, And tell you exactly where you are.

3. In addition to receiving different feeding treatment programs in the PACU, the two groups received the same care and diet program formulated by the same care group.

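### The arms differ in when ward feeding may begin as well as in the carbohydrate drink, although the protocol says the diet is otherwise the same, so a prealbumin difference cannot be credited to the drink alone

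*Protocol*

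**What the plan says.** Item 3 at the end of section 3.1.2 describes the contrast between the arms: "In addition to receiving different feeding treatment programs in the PACU, the two groups received the same care and diet program". On its plain reading, feeding in the PACU is the only planned difference.

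Earlier in section 3.1.2 each arm has its own rule for the ward:

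- **Group C**, after 60 min of observation following extubation: "returned to the ward for fasting and fasting for at least 6 h, and began to eat gradually through the mouth after anal exhaust". This rule is printed twice.
- **EOF group**, after the drink in the PACU: "After the patient returned to the ward, the liquid diet began to gradually overenter the normal diet". No minimum fast and no flatus condition is given. The next sentence breaks off before it is complete.

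The effect to be estimated is worded as that of the carbohydrate. The title is "Effect of Postoperative Oral Carbohydrate Administration in Total Knee Arthroplasty", objective 1.1.1 is "To evaluate the effect of oral carbohydrates early after TKA on the nutritional status of elderly patients", and section 2 expects that "Oral carbohydrates in the early postoperative period can improve patient nutritional" status, comfort and satisfaction. The primary endpoint (1.2.1) is fasting prealbumin on the day of surgery, day 1 and day 3.

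**The concern.** The ward rules operate after the patient has left the PACU, so the exception in item 3 does not cover them. If the rules are followed as written, EOF patients receive the drink and may also start ward food earlier. Both components always occur together in one arm and are both absent from the other, and no analysis of two such arms can separate them.

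What is at stake is the conclusion, not the validity of the randomised comparison. A favourable day 1 or day 3 prealbumin result would be reported as an effect of oral carbohydrate when it might come partly or wholly from earlier ordinary feeding. The protocol itself makes this rival explanation plausible: the background (section 1) credits early return to eating and drinking with benefits of its own, and argues for carbohydrate drinks separately.

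The comfort claim in section 2 has the same weakness. One of its measures is the "NRS score of thirst and hunger at 2h, 6h and 8h after surgery", and the ward rules differ during that window.

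**Working it through.** The protocol states no figure on this point to reproduce. The check sets the rules side by side and then sizes the gap.

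**1. Components by arm (section 3.1.2)**

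| Component | EOF | Group C |
|---|---|---|
| Carbohydrate drink in PACU | yes, 5 ml/kg | no |
| Minimum ward fast | none stated | at least 6 h |
| Flatus required before food | not stated | yes |
| Ward food starts | liquids after ward return, no clock time | after both conditions are met |

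The drink and the ward start rule both differ. Item 3 allows only the first.

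**2. Can another reading of item 3 remove the difference?**

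- *The EOF ward sentence applies to both arms.* It would then contradict Group C's explicit fast.
- *The same diet means the same menu once eating resumes.* The start rules still differ.
- *The PACU programmes include their continuation on the ward.* The literal conflict goes, but the intervention is then a bundle that the title, objective 1.1.1 and section 2 do not name.

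**3. Size of the gap in permitted ward intake, in hours after extubation**

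- Group C, fast counted from extubation: 6 h.
- Group C, fast counted from ward return after the 60 min observation: 1 + 6 = 7 h.
- EOF ward liquids: no time is given. Assumed 1 to 3 h; the protocol allows up to 2 h for finishing the drink.

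| Group C earliest | EOF at 1 h | EOF at 3 h |
|---|---|---|
| 6 h | 6 − 1 = 5 h | 6 − 3 = 3 h |
| 7 h | 7 − 1 = 6 h | 7 − 3 = 4 h |

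The range is 3 to 6 h. It is a lower bound within the assumption, because Group C must also wait for first flatus, which has no stated upper limit and is itself a secondary endpoint (1.2.2.1, item 6).

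**4. Timing against the endpoints**

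- Day 1 and day 3 prealbumin are sampled after the ward rules may have diverged.
- Extubation does not precede the end of surgery, so 6 h after surgery is no later than 6 h after extubation. The 6 h hunger and thirst score therefore falls at or before Group C's earliest permitted food, when EOF patients may already be taking ward liquids.

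**5. Size of the drink, for scale only**

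For an assumed 70 kg patient the volume is 5 × 70 = 350 ml. Section 3.1.2 gives two concentrations: "The EOF group drank 10.5% of 5 ml/kg body weight (100ml containing 12.5g maltodextrin, fructose and glucose" against 12.5% in the next paragraph. That yields 350 × 0.105 = 36.75 g or 350 × 0.125 = 43.75 g of carbohydrate. The conflict between the concentrations is a separate matter that must also be reconciled; nothing here depends on it.

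**The case against.** The strongest reply is that the bundle is the intended design. Both ward rules sit under the PACU management text where patients are allocated, so the PACU feeding programmes in item 3 could mean the whole programme assigned there, including its ward continuation. The arm names refer to early and conventional feeding, the background is motivated by routine postoperative fasting of at least 6 h, and objective 1.1.1 never says the drink alone. On this view the fault is one loosely translated sentence. This reduces the weight of the literal contradiction. It does not help with attribution: under this reading the intervention is expressly a bundle, while the title, objective and expected result still name only oral carbohydrate.

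A second reply is that the EOF text is damaged, gives no start time, and may have lost a condition. The missing start time is a real limit on any calculation. The broken sentence, however, opens with the patient already able to tolerate a normal diet, which is after ward feeding has begun, so it is unlikely to have held a common start rule.

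A third reply is that the hours are assumed and concern permitted intake, not actual intake. This stands. A later EOF start would shrink the gap below 3 h, and nothing in the protocol turns hours of feeding into a change in prealbumin.

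**Conclusion.** The concern holds. As written, section 3.1.2 gives the arms different ward feeding start rules, and item 3 says the diet is the same outside the PACU. The trial can validly compare an early feeding strategy with conventional fasting. It cannot attribute a prealbumin or comfort difference to the carbohydrate drink alone, which is how its title, objective 1.1.1 and section 2 are worded.

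The minimum gap in permitted ward intake is 3 to 6 h if EOF ward liquids start 1 to 3 h after extubation. That range rests on the assumed start and on whether Group C's fast runs from extubation or from ward return. The attribution problem itself rests on neither; it follows from the difference in start rules. The drink's share of any effect cannot be computed. This should be corrected, but it does not invalidate the randomised comparison.

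**What to change.** Reconcile item 3 of section 3.1.2 with the arm descriptions above it, in one of two ways.

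- **If the ward start rules are meant to differ:** remove or qualify item 3, and word the title, objective 1.1.1 and section 2 as the effect of an early oral feeding strategy (carbohydrate drink plus earlier ward feeding) against conventional fasting.
- **If they are meant to be the same:** state that one ward feeding rule applies to both arms. Which rule is for the investigators to decide.

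In either case, complete the broken EOF sentence and state from which moment Group C's fast is counted. Record the time of first oral intake and of first ward meal in both arms if the case report form does not already do so; the list in section 3.1.3 names neither.

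The cost is protocol wording and at most two time fields. The downside is that, unless ward feeding is aligned, the conclusion will concern a feeding strategy and not the carbohydrate product.

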3.1.3 The Follow-up Period

Record: Patients had fasting serum prealbumin, retinol-binding protein levels, and

insulin resistance index on the same day, 1 day and 3 days after surgery.

Record: 2 hours, 6 hours and 8 hours postoperative digital scores; bloating, hypoxemia and reflux aspiration occurred 24 hours after surgery.

Record: length of hospitalization, first anal exhaust time, first ambulation time, nausea and vomiting, and patient satisfaction.

4. Subject recruitment and protective measures

4.1 Inclusion criteria

- Patients undergoing elective knee replacement surgery;
- the patient gave informed consent;
- Age ≥ 65 years, Sex is not limited
- American Society of Anesthesiologists(ASA)I~III level
- Body Mass Index(BMI)18~28kg/m²

4.2 Exclusion criteria

- Preoperative gastric emptying disorders, such as gastroesophageal reflux or previous surgery;
- Diabetes mellitus, severe renal insufficiency, or other severe metabolic diseases;
- History of motion sickness;
- Mental disorders, alcoholism, or a history of substance abuse;
- Patients with abnormal swallowing function;
- Maltodextrin, fructose allergy or intolerance;
- Surgery time was greater than 3 hours.

4.3 Exit criteria

Patients may withdraw their informed consent and withdraw from the trial at any time.

The investigator may decide on the subject to terminate the withdrawal from the study in the following circumstances.

Any medical condition in the study leads to the risk of continuing the study subjects; Subjects receive analgesic treatment other than the prescribed analgesic remedy protocol, and other subjects who fail to complete the test as specified in the test protocol;

The investigator judged the other conditions that should be withdrawn from the trial.

5 Informed consent

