7.2 Retention of the records

The investigator shall keep all the detailed original documents of the subject and record the trial process, medication status, laboratory examination data, safety data and efficacy assessment in the case report form. The recorded data shall be complete, timely and clear. The original documents and medical records should be clear, detailed

and easily identified by those participating in this clinical trial.

The case report form and the original files can only be modified by the investigator. No modification to the case report form and the original file shall smear the original data off. The correct way to modify is to line the original data, and then write the modified data next to the original data, and sign the date and the name of the modification.

Test data shall be retained until 5 years after the termination of the test.

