7.4 Research, supervision and inspection

7.4.1 Research supervision

Inspectors must follow the drug clinical trial quality management specification (GCP) and standard operation procedures (SOP), visit the research unit regularly or according to the actual situation, supervise the clinical trial work and progress, check, confirm all data records and reports, correct and complete, consistent with the original data, ensure the clinical trial in accordance with the clinical trial protocol, the researchers should actively cooperate with the inspectors. The specific contents of the inspector include:

- a) Ensure that the test undertaking unit has appropriate conditions, including staffing and training, complete laboratory equipment, good operation, various inspection conditions related to the test, an estimated sufficient number of subjects, and the participants to be familiar with the requirements in the test plan;
- b) Monitor the implementation of the trial program during the trial, confirm that the informed consent of all subjects is obtained before the trial, understand the enrollment rate of the subjects and the progress of the trial, and confirm that the selected subjects are qualified;
- c) Confirm that the records and reports of all data are correct and complete, and that all case report forms are entered correctly and consistent with the original data. All errors or omissions have been corrected or indicated, signed and dated by the Investigator.
- d) Verify that all adverse events are recorded, and that serious adverse events shall be reported and recorded within the specified time;
- e) Clearly and truthfully record the failed visits, un-conducted tests, and undone checks should be made, and whether the errors and omissions should be corrected;
- f) The written inspection report shall be completed after each visit, which shall state the date, time, name of the inspector, the findings of the inspection, etc.

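### Section 4.3 lets the investigator take randomised patients out of the study for departing from the protocol, and does not separate departing from the assigned feeding from leaving follow-up

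*Protocol*

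**What the plan says.** Section 4.3 first allows patients to withdraw consent at any time. It then gives the investigator a separate power: "The investigator may decide on the subject to terminate the withdrawal from the study in the following circumstances". The translation is poor, but the heading and the closing line make clear that this is an exit rule. Besides medical risk, the grounds are:

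- **Non-completion:** "other subjects who fail to complete the test as specified in the test protocol"
- **Analgesia:** "Subjects receive analgesic treatment other than the prescribed analgesic remedy protocol"
- **Open-ended discretion:** "The investigator judged the other conditions that should be withdrawn from the trial"

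The exit is from the study or the trial as a whole. Stopping or departing from the assigned feeding while staying under observation is not mentioned.

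The related sections say the following:

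- **Section 3.1.2:** patients are randomised on entering the PACU. Carbohydrate (EOF) patients take 30 ml and then finish the drink within 2 h. Controls fast for at least 6 h and eat after first passing gas.
- **Section 1.2.1:** the primary endpoint is prealbumin on the day of surgery, day 1 and day 3.
- **Section 1.2.2.2:** safety covers "The incidence and severity of various adverse events (AE) from the start of oral carbohydrates to the end of the trial".
- **Section 3.1.3:** the records include "bloating, hypoxemia and reflux aspiration occurred 24 hours after surgery", with no adherence condition.
- **Section 7.4.1, item e:** "Clearly and truthfully record the failed visits, un-conducted tests, and undone checks should be made".

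**The concern.** A patient who cannot finish the drink, or who breaks the fast, is still a randomised patient. That patient's tolerance, safety and prealbumin are part of what the trial sets out to compare. Section 4.3 can be read as allowing the investigator to remove such a patient, and no other section keeps a removed patient in the scheduled assessments.

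The tasks differ by arm, so removals could differ by arm. Reasons for failing a task, such as poor tolerance or slow recovery, could relate to the outcome. The retained groups would then no longer be the randomised groups.

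How withdrawn patients are analysed can be left to a statistical analysis plan. Who stays in follow-up is a matter of conduct that the protocol fixes, and a blood sample that was never drawn cannot be recovered later.

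A related wording problem is that the analgesia ground depends on a prescribed analgesic remedy protocol that section 3.1.2 does not identify. That section describes parecoxib, two nerve blocks and hydromorphone patient-controlled analgesia with parameters adjusted according to pain. It is therefore unclear which treatment would count as outside the protocol. As written, this ground is the same in both arms. It adds to loss of data but does not itself create an arm difference.

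**Working it through.** **Reading the sections together**

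1. Allocation is at PACU entry (3.1.2), so any departure from the drink or the fast comes after randomisation.
2. The feeding steps (2 h for the drink, at least 6 h for the fast) come before the day 1 and day 3 samples (1.2.1). The 24 h assessments (3.1.3) and adverse events to the end of the trial (1.2.2.2) also extend beyond these steps.
3. An exit under 4.3 can therefore come before most of the outcome data.
4. Section 3.1.3 lists the assessments and nothing orders them to stop, but nothing says they continue after an exit. Item e of 7.4.1 is a monitoring duty to record what was not done. Its wording is garbled, and it does not clearly require a missed assessment to be obtained.

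**How large the effect could be**

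The protocol states no figure to reproduce: it gives no sample size, SD, alpha or exit rate. Every input below is an assumption:

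- no true effect, and a normal outcome with SD 1 among retained patients
- n per arm of 30, 50 or 100
- proportions p_EOF and p_C exit and are not measured
- those who exit lie d SD below those retained in their arm
- two-sided 5% z test

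If a proportion p exits, the retained mean exceeds the full-arm mean by p × d. The spurious difference between arms and its standard error are then:

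- shift = d × (p_EOF − p_C)
- SE = √[1/(n(1 − p_EOF)) + 1/(n(1 − p_C))]
- type I error = Φ(−1.96 + shift/SE) + Φ(−1.96 − shift/SE)

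Worked case: n = 100, p_EOF = 0.10, p_C = 0, d = 1. The shift is 0.10 and SE = √(1/90 + 1/100) = 0.1453, so shift/SE = 0.688 and the type I error is 0.1058.

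| Exits (EOF / control), d | n = 30 | n = 50 | n = 100 |
|---|---|---|---|
| 5% / 0%, d = 0.5 | 0.0510 | 0.0517 | 0.0535 |
| 10% / 0%, d = 1 | 0.0664 | 0.0775 | 0.1058 |
| 10% / 5%, d = 1 | 0.0540 | 0.0566 | 0.0633 |
| 10% / 10%, d = 1 | 0.0500 | 0.0500 | 0.0500 |

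Swapping the arms gives the same sizes with the opposite sign.

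**Would baseline adjustment remove it?**

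Suppose the day-of-surgery sample is a baseline and correlates 0.5 with the later value. The SE is multiplied by √(1 − 0.5²) = 0.866, which gives 0.1258 in the worked case. The shift is multiplied by the share of the gap that baseline does not explain.

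| Share not explained by baseline | Shift | Type I error |
|---|---|---|
| 0 | 0 | 0.0500 |
| 0.5 | 0.05 | 0.0683 |
| 1 | 0.10 | 0.1249 |

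A simulated analysis of covariance with 8,000 runs gave 0.054 with the gap wholly at baseline and 0.125 with it wholly after baseline. Adjustment therefore protects only against exits driven by baseline level.

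**The case against.** The strongest objection is about meaning. The protocol often uses the word test for the trial itself, as in "Test data shall be retained until 5 years after the termination of the test" (section 7.2). On that reading the non-completion clause may cover only patients who drop out, not those who fail the drink or the fast. The power is also discretionary, and section 3.1.3 schedules assessments without any adherence condition. Further, the drink is taken with the patient's consent after a wakefulness check and a 30 ml swallow trial. A patient who fails the check or declines may therefore still be within protocol. Both feeding steps are short, and nothing shows that an investigator would remove such a patient before day 1. Finally, every magnitude is assumed. Marked inflation needs one-sided 10% exits with a full 1 SD gap, and the milder cases are close to nominal.

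Much of this stands. The narrow reading is possible, no exit is compulsory, and no bias has been shown. Three things remain:

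- The clause refers to completion as the protocol specifies, and the protocol specifies the feeding, so the wider reading is not excluded.
- The analgesia ground names a departure from protocol as a reason to leave the study, whatever the other clause means.
- Discretion is a weak safeguard when drinking versus fasting is visible and the protocol describes no blinding.

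**Conclusion.** The concern holds. Section 4.3 is a badly fixed conduct rule: it allows randomised patients to be removed from the study for departing from the protocol, and nothing keeps them in the day 1 and day 3 bloods or the later safety records. It should be fixed. Confidence is medium, because the meaning of the non-completion clause is uncertain and the power may seldom be used.

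The size and direction of any bias cannot be worked out from the document. Under the stated assumptions the unadjusted type I error runs from 5.0% (equal exits) to 10.6% (10% EOF-only exits, 1 SD gap, 100 per arm). It reaches 12.5% with baseline adjustment if none of the gap is explained by baseline. There is no bias if exits are unrelated to outcome.

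**What to change.** Amend section 4.3 as follows:

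1. Treat not completing the assigned feeding, and analgesia outside the protocol, as recorded protocol deviations and not as grounds for leaving the study.
2. State that these patients, and any whose feeding is stopped by the clinician, still have the scheduled day 1 and day 3 bloods and the 24 h assessments unless they withdraw consent to follow-up.
3. Say whether the non-completion clause refers to the trial or to the assigned feeding.
4. Reconcile the analgesic remedy protocol named in 4.3 with the analgesia described in 3.1.2.

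Decisions on feeding and analgesia stay with the treating clinician; the change governs only who remains in follow-up.

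The cost is protocol wording, since the bloods and assessments are already scheduled for every patient. The drawback is slight dilution. If 5% or 10% of one arm receives none of the effect, the measured effect is 1 − 0.05 = 95% or 1 − 0.10 = 90% of the full one.
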